Breach of confidentiality: There is a risk of breach of confidentiality. In order to protect against this risk, all data will be stored on a secure, password protected network. All data will be identified using unique identification numbers, not names, date of birth, or other identifiable information. In files where identifiable information is linked to the unique ID number, only staff members who specifically use this information for contacting participants, etc. will have access.

Email address: We are requesting the subject's email address so we can communicate study visit reminders or changes with them. Email is generally not a secure way to communicate about a subject's health as there are many ways for unauthorized users to access email. The subject is instructed to avoid sending sensitive, detailed personal information by email. Email should also not be used to convey information of an urgent nature. If the subject needs to talk to someone immediately, they are instructed to contact a pulmonary research study coordinator at [contact]. Or can also contact the Principal Investigator of the study [name] at [contact]. The subject does not have to provide their email address to participate in this study. The subject can also request at any time that email no longer be used to communicate about the study, without any loss or penalty.

Sample Size Calculation and Data Analysis:

This is a pilot study. Our target sample size is total 30 individuals with severe asthma. The attrition rates in our prior research have been low (0-7%) and our power calculations assume that at least 22 subjects (12% attrition) complete the study. For continuous outcomes in general, including airway cellular and molecular inflammatory responses to stimulation, and measures of neural activity (e.g. % signal change in insula by fMRI), effect sizes for the relationship between neural activity and increases in inflammatory markers is expected to be large. In previous studies, we report associations between increases in activity in insula and ACC and peripheral measures of inflammation with effect sizes that range from .56 to .99. It should be noted that the extremely large effect sizes are, in part, a function of the small sample size and thus, the

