confidence interval for the population statistic is quite large. Nonetheless, these relationships were replicated in a subsequent investigation with robust, though smaller, effect sizes. Based on these preliminary studies, we expect to have very high power (>.85) to detect an association of moderate magnitude (.5) between neural activity and peripheral biological markers across groups with the proposed sample size. Data from individuals with severe asthma will be compared with data from individuals with mild to moderate asthma, as well as non-asthmatics.

a. Comparison to other study populations. Data from subjects with severe asthma will be compared with data from individuals with mild-to-moderate asthma, as well as non-asthmatic subjects. These data have been collected under protocol 2014-0116. The data has been collected but not yet analyzed in relationship to other severities of asthma. The data and samples were collected in the same way the data and samples will be collected under the current study.

b. Utilization of SARP data. Subjects who enroll into this study will also have SARP (2012-0571) data that will be utilized. The SARP Data Coordinator Center and the SARP Steering Committee has a Data Sharing Policy. Briefly, all data collected by a specific site, can be utilized at that site for other purposes. A SARP Data Request Form is completed and submitted to the Steering Committee for approval. Information requested on the Data Request Form includes, requesters, site affiliation, main hypothesis, rationale, description of the data requested (time points and type of data (spirometry, questionnaires, etc)), and the format being requested. This request form is reviewed first by the Publications Committee and secondly by the Steering Committee. A Data Request will be made for SARP data to accompany any subject who enrolls into this study. Data to be requested for this comparison analysis will include demographics, lung function testing, questionnaire data, sputum cell count and differential, medication use, and other data as deemed appropriate by the PI or designee.

Data Storage:

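### 22 completers, 12% attrition and a target of 30 do not agree, and 22 completers do not give the stated power of >.85 if .5 is a within-group correlation tested at alpha .05

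*Combined protocol and SAP*

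**What the plan says.** All the relevant text is in *Sample Size Calculation and Data Analysis* in the combined protocol and SAP.

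- Target: "Our target sample size is total 30 individuals with severe asthma".
- Completers: "our power calculations assume that at least 22 subjects (12% attrition) complete the study". The same sentence puts attrition in the team's earlier research at 0 to 7%.
- Earlier results: the team reports "associations between increases in activity in insula and ACC and peripheral measures of inflammation with effect sizes that range from .56 to .99". It adds that the largest of these partly reflect small samples.
- Power: "we expect to have very high power (>.85) to detect an association of moderate magnitude (.5"), described as an association "between neural activity and peripheral biological markers across groups with the proposed sample size".
- Comparison data on mild-to-moderate asthma and on people without asthma: "These data have been collected under protocol 2014-0116". The sizes of these groups are not given.

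The section does not say whether .5 is a correlation, a standardised mean difference or another metric. It also gives no alpha, sidedness, test or analysed number.

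**The concern.** There are two problems, of different strength.

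The first needs no assumption. The parenthesis equates 22 completers with 12% attrition, but against a target of 30 the two figures do not match.

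The second is conditional. The text ties its power calculations to 22 completers. Because it speaks of associations between neural activity and inflammatory markers, a correlation is the natural reading of .5, though the text does not establish it. On that reading, at the conventional alpha of .05, 22 looks too few for power above .85.

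This is the plan's only justification of sample size. As it stands, a reader cannot tell whether 22, 26 or 30 completers support the power statement. If the within-group reading is the intended one, the chance of missing a true correlation of .5 with 22 completers is about 31% two-sided or 21% one-sided, where the plan implies under 15%.

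**Working it through.** **Inputs from the plan:** target 30; at least 22 completers; 12% attrition; prior attrition 0 to 7%; association .5; power >.85. **Assumed, because not stated:** alpha .05, with both one-sided and two-sided tests tried.

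**Step 1. Attrition**

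- 22 completers of 30: 1 − 22/30 = 26.7%.
- 12% attrition from 30: 30 × .88 = 26.4, so about 26 completers.
- 22 completers at 12%: 22/.88 = 25 enrolled.
- Prior attrition of 0 to 7% from 30: 30 × .93 = 27.9, so 28 to 30 completers.

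The pair 22 and 12% is reproduced only with 25 enrolled.

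**Step 2. Power for a within-group correlation of .5**

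Three formulas were used.

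- *Fisher z, two-sided:* power = Φ(atanh(.5) × √(n − 3) − 1.960). With n = 22: .5493 × √19 = 2.394; 2.394 − 1.960 = .434; Φ(.434) = .668. One-sided, with 1.645 in place of 1.960: Φ(.749) = .773.
- *Exact, both variables random (bivariate normal):* given W, the test statistic is noncentral t with n − 2 degrees of freedom and noncentrality (.5/√.75) × √W, where W is chi-square with n − 1 degrees of freedom. Power is averaged over W.
- *Fixed predictor:* noncentral t with n − 2 degrees of freedom and noncentrality (.5/√.75) × √n. With n = 22 the noncentrality is .577 × 4.690 = 2.71.

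Results, two-sided / one-sided at .05:

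| n | Fisher z | Exact | Fixed predictor |
|---|---|---|---|
| 22 | .668 / .773 | .688 / .793 | .731 / .834 |
| 26 | .750 / .839 | .767 / .854 | .806 / .888 |
| 28 | .784 / .865 | .799 / .877 | .837 / .908 |
| 30 | .814 / .887 | .828 / .897 | .863 / .925 |
| First n reaching .85 | 33 / 27 | 32 / 26 | 29 / 24 |

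A simulation of 200,000 replicates agrees with the exact column: .688 / .794 at n = 22 and .827 / .896 at n = 30.

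At n = 22 no entry reaches .85. For exact power of .85 there, alpha would have to be .152 two-sided or .076 one-sided. The correlation detectable with 85% exact power (two-sided / one-sided) is .59 / .54 with 22, .55 / .50 with 26 and .51 / .47 with 30.

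**Step 3. Other readings of .5 with 22 completers**

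| Reading | Power |
|---|---|
| Correlation, one-sided alpha .10, exact | .88 |
| f² = .5, one predictor | .88 |
| Three-group ANOVA, f = .5, 22 per group | .95 |
| Mean difference of .5 SD, 22 per group, two-sided | .37 |

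**Step 4. Pooling with the comparison groups**

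The exact two-sided calculation first passes .85 at a total of 32 (power .853), or 34 if two group terms are in the model (treated as N − 2). Without group terms, this takes 32 − 22 = 10 comparators added to 22 completers, 6 added to 26, or 2 added to 30. With two group terms it takes 12, 8 or 4. The plan does not say how many comparators there are.

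**The case against.** The strongest reply concerns the power claim. The text refers to an association "between neural activity and peripheral biological markers across groups with the proposed sample size", which may mean an analysis pooled with the earlier protocol's data, or at least the full 30. At 30 the claim roughly holds: two-sided power is .83 exact and .86 with a fixed predictor, and one-sided it is above .85 by every formula. Pooling would need only a handful of comparators. This stands: the power statement has not been refuted, and what can be said about it is conditional.

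A second reply is that the text says at least 22, so 22 may be a cautious floor, and 30 enrolled with 26 completing would satisfy it. That is fair as far as it goes, but then the 12% label attached to 22 is wrong. A related point is that 22 and 12% agree exactly with 25 enrolled, so 30 may be the figure out of line. The documents do not say which of the three is out of date.

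Third, the practical effect is small. This is a pilot, prior attrition would leave 28 to 30 completers, the text itself warns about inflated earlier effects, and no decision depends on .85. That limits the weight of the point without removing the need to correct it.

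**Conclusion.** The concern holds. Without any assumption, 22 completers, 12% attrition and a target of 30 are inconsistent: the gap is about four completers (26 against 22), or 26.7% attrition against 12%.

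Conditionally, for a within-group correlation of .5 at alpha .05, the 22 completers on which the plan says its calculations rest do not give power above .85, one-sided or two-sided, by any of the three formulas. The shortfall ranges from about 2 percentage points (one-sided, fixed predictor) to 18 (two-sided, Fisher z); on the exact two-sided calculation it is about 16. At 30 completers any shortfall is marginal, arises only two-sided, and depends on the formula.

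Which power actually applies turns on the metric, alpha, sidedness and analysed number, which only the sponsor can state. This should be fixed, but it does not threaten the conduct of the pilot.

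**What to change.** 1. Keep 30, the only enrolment target stated, and make the completer and attrition figures agree with it: for example, 12% of 30 leaves about 26 completers. If 22 is meant as a floor, label it as 26.7% attrition.
2. State what .5 measures, together with alpha, sidedness, the test and the number analysed.
3. Restate the power to match. For a within-group correlation at two-sided .05, that is about .69 with 22 completers, .77 with 26 or .83 with 30; alternatively, say that 22 completers give 85% power for a correlation of about .59. If a fixed-predictor calculation was used, say so and give .73, .81 or .86. If the test is one-sided, the exact values are .79, .85 or .90.
4. If a pooled analysis is meant, give the number of comparators, base the power on severe-asthma completers plus that number, and say whether group terms enter the model.

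The cost is a few sentences, with no extra patients and no change in procedures. The stated power becomes less favourable at 22 completers unless pooling, a larger completer number or another metric is confirmed.
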